8.8. Staged Procedures

Treatment of all target lesions with the Resolute Onyx stent within a single PCI is encouraged, if reasonable and safe. However, when staging is required for clinical reasons, the staged procedures should be performed within 30 days from index procedures and similar to index procedure, with a Resolute Onyx stent. A staged procedure is considered a subsequent treatment of a lesion in a vessel not treated at index that is present at the time of the index procedure. Staging should be pre-specified at the time of the index procedure ~~and follow-up should be calculated from the date of index procedure~~. Cardiac enzymes should be obtained before and after the staged procedure, with the same steps as that taken for the index procedure. Lesions and vessels treated with Resolute Onyx stent at the staged procedure are considered target lesions and vessels.

In addition, staged procedures should meet the following requirements:

- Staged procedures must be pre-specified at index procedure AND completed within 30 days of index procedure to qualify as a planned staged procedure. Any additional procedure to the index procedure that does not meet these requirements may be considered as a revascularization and follow-up will be based on the timing of index procedure.
- Resolute Onyx stents should be used at both index and at staged procedures.
- Staged procedures in the target vessel(s) treated at index are NOT allowed.
- Staging should not involve a segment directly adjacent to a segment treated during the index PCI.
- Every urgent coronary reintervention before the planned staged procedure is considered an event.
- Duration of DAPT is one month following the staged procedure.
- For one-month clear analysis, the "clear" definition should be extended to one month beyond the planned staged procedure.
- Follow-up for the one month and two month time points will be calculated from the date of staged procedure; remaining follow ups will be calculated from the index procedure.

8.9. Bailout

For subjects who consent prior to procedure, bailout procedures should be avoided unless required for subject safety. If bailout procedures are performed, justification should be documented on the eCRF.

If a subject in this study experiences a major dissection or an occlusive complication (as evidenced by decreased target vessel flow, chest pain, or ischemic ECG changes which do not respond to standard rescue techniques), bailout procedures may be performed. For these events occurring during the study procedure, additional stenting with the Resolute Onyx DES may be employed as a bailout treatment. In the event a Resolute Onyx DES cannot be implanted, the operator may deploy another device at Investigator's discretion to complete the procedure successfully. Subjects with bailout non-study stent(s) will be followed for ITT analysis through one year and DAPT is per physician discretion.

Target lesion(s) is/are to be selected with the intent to cover each lesion with a single stent. If incomplete coverage occurs during the procedure, additional stenting with assigned study stents may be employed to provide complete coverage.

Refer to IFU for procedural guidelines.

8.10. Treatment Failure

Study stent(s) that enter the guide catheter and fail to be implanted at the intended location are considered treatment failures and should be recorded in the eCRF. Treatment failures should be followed-up for safety purposes through one year and these subjects and lesions will be included in the ITT population but not the primary analysis. Subjects experiencing total treatment failure (i.e., no Resolute Onyx stent treatment) will not be replaced. After the one-year time frame, total treatment failures should be exited from the study.

8.11. Assessment of Effectiveness

Assessments of effectiveness will include acute device, lesion, and procedural successes as well as adjudication of any revascularizations reported through each subject's follow-up.

8.12. Assessment of Safety

Reports of all adverse events related to endpoint (including bleeding), SAEs, adverse device effects and device deficiencies, with the return of the device when possible, will be evaluated by Medtronic. The Clinical Events Committee (CEC) will review and adjudicate clinical events possibly related to study endpoints that need adjudication throughout the duration of the study.

8.13. Recording Data

Data collected on each subject will be recorded on a web-based eCRF. This study will utilize an Oracle Clinical Remote Data Capture (RDC) system that is the property of Medtronic. Each enrolled subject is assigned a unique study ID number. Records of the subject/subject ID relationship will be maintained by the study site. Individual subject medical information obtained as a result of this study will be considered confidential.

Authorized site personnel as indicated on the Delegation Task List (DTL) will record the required data on eCRFs. Study personnel delegated for eCRF completion and/or approval per the DTL will be trained on the use of the RDC system and thereafter be provided with a user name and password to access the system. Passwords are individual and cannot be shared.

The eCRFs must be completed and updated to reflect the latest observations on the subjects participating in the study. The investigator (or delegated personnel by investigator) will electronically sign the appropriate pages of each eCRF. In the U.S. the delegated personnel will be an approved sub-investigator, and in Japan this may be study staff that has been delegated to enter information into the electronic data system as a copy from medical records or other materials. The Oracle Clinical RDC

Medtronic Controlled Information

system maintains an audit trail of entries, changes, and corrections in eCRFs. If a person only authorized to complete eCRFs makes changes to an already signed eCRF, the investigator shall re-approve this eCRF.

The hospital files (electronic or paper) will constitute source data. For the purpose of adjudication of events by the CEC, relevant event-related source documents (e.g. angiograms, procedural details, worksheets, etc) will be redacted and collected for events that need to be adjudicated by the CEC. In Japan, availability of source documentation may be limited due to hospital policies. If a specific source document is not available, necessary information may be transcribed on to the relevant CRF page.

The eCRFs may not serve as source documents. Source documentation for data elements not routinely captured in medical records (e.g., angiogram variables, procedural details) may vary from center to center.

The principal investigator is responsible for ensuring that all sections of each CRF are complete and correct and that those entries can be verified against source data.

Medtronic will be responsible for the processing and quality control of the data. Data review, database cleaning and issuing and resolving data queries will be done according to Medtronic internal SOPs and the Data Management Plan for this study. The study database will employ validation programs (e.g., range and logic checks) on entered data to identify possible data entry errors and to facilitate data validation.

8.14. Investigator records

At a minimum, the following records must be kept by the investigator:

- All approved versions of the Clinical Investigation Plan
- Medtronic- and IRB- approved Informed Consent Form
- Fully signed Clinical Trial Agreement and confidentiality agreement (if not included in the Clinical Trial Agreement) (for US sites)
- Financial disclosures: if the financial interests change during the course of the study or within one year of completion of the study, the investigator is obliged to inform the sponsor of such financial change
- Insurance certificates, if applicable
- Completed Delegated Task List and Curriculum Vitae of all investigational site personnel
- Training documentation of all investigation site personnel
- Relevant communications
- Subject screening log and subject identification log
- Signed, dated, and fully executed Informed Consent Forms
- The investigator will clearly mark clinical records to indicate that the subject is enrolled in this clinical investigation.
- Lab certificates / Lab normal ranges
- Fully executed eCRFs and corrections (in the EDC or as copy on site)
- Reports of Adverse Events and Device Deficiencies
- IRB approval letter, voting list and correspondence
- Clinical Study Report (including statistical analysis), if applicable

8.15. Investigator reporting responsibilities

The investigator is responsible to ensure that all work and services related to this trial described herein, or incidental to those described herein, are conducted in accordance with the highest standards of medical and clinical research practice, the requirements of the IRB, the investigational plan, the terms of the Investigator Agreement, and all applicable local laws and regulations, including (except in Japan):

- 21 CFR 812: Investigational Device Exemptions
- 21 CFR 50 (Subpart B): Informed Consent of Human Subjects (21 CFR 50.20 General Requirements for Informed Consent)
- 21 CFR 54 (Part 54): Financial Disclosure by Clinical Investigators

Table 4 describes the Investigator reporting responsibilities.

Table 4. Investigator Reporting and Data Submission Responsibilities

Report / Data Submission	Submit to	Description/Constraints
CRFs (screening failure, inclusion/exclusion, baseline, follow-up, non-compliance, event, study exit)	Sponsor	Submit via EDC (guidelines: within 7 days)
Angiographic media	Angiographic Core Laboratory	Submit to Core Laboratory (guidelines: within 7 days)
Adverse Events	Sponsor & IRB	Refer to Section 10 for reporting requirements
Progress Report	Sponsor & IRB	Provide if required by local law or IRB
Withdrawal of IRB approval	Sponsor	Investigator must report a withdrawal of the reviewing IRB within 5 working days of the investigator's part of the investigation.
Final Report	IRB	This report must be submitted within 3 months after termination or completion of the investigation or the investigator's part of the investigation, or per local IRB requirements.
Deviations from Investigation Plan		
Deviation from Investigation Plan (Other – Non-Emergent)	Sponsor & IRB	If the deviation may affect the scientific soundness of the plan or the rights, safety and welfare of the subjects (and is not an emergency), then the deviation must be approved by Medtronic and the reviewing authority prior to its implementation. If the deviation does not affect these issues (study soundness, rights, safety, etc.) then only Medtronic must approve it

Deviation from Investigation Plan (Emergency)	Sponsor & IRB	Notification must be made as soon as possible if the deviation was made to protect the life or physical well-being of a subject in an emergency
Failure to Obtain Informed Consent (not required for Japan sites)	Sponsor & IRB	The Investigator must notify Medtronic and the reviewing authority within 5 working days after device use. The report must include a brief description of the circumstances justifying the failure to obtain informed consent.

8.16. Sponsor record maintenance responsibilities

At a minimum, the sponsor will keep the following records:

- All essential correspondence related to the clinical study
- Signed Investigator Agreement
- Current curriculum vitae for each Principal Investigator at all sites
- Current curriculum vitae for all other investigators and site team members (for US sites)
- Delegated Task List (DTL)
- SAE, AEs related to endpoint (including bleeding), adverse device effects, and device deficiency information
- All data forms, prepared and signed by the Investigators, and received source documentation and core lab reports
- Clinical investigation protocol and subsequent amendments
- Site monitoring reports
- Financial disclosure information
- Study training records for site participants and internal trial staff members
- Contact lists of all participating investigators/investigative sites, IRB information, study monitors and Sponsor staff members including the medical expert; Sponsor will maintain these lists and provide updates to the necessary parties.
- Sample of device labeling
- Insurance certificates, if applicable
- IRB approval documentation and voting list and correspondence
- Lab certificates (except in Japan) / Lab normal ranges
- Statistical analyses
- Clinical Investigation Report

8.17. Sponsor reporting responsibilities

Sponsor reporting requirements are summarized in Table 5.

Table 5. Sponsor Reporting Requirements

Report	Submitted to
--------	--------------

Serious Adverse Event (SAE) Adverse Device Effect (ADE) or Device Related Adverse Event Device Deficiency that might have led to a SADE	Regulatory authorities: Reporting timeframe as per local requirement. IRB: Reporting timeframe as per local IRB requirement.
Serious Adverse Device Effects (SADE) Unanticipated Adverse Device Effect (UADE) Unanticipated Serious Adverse Device Effect (USADE)	Regulatory authorities: Submit as soon as possible, but not later than within 10 working days after the Sponsor first receives notice of the event, as per local reporting requirement. IRB: Reporting timeframe as per local IRB requirement.
Study enrollment status and rates of cardiac death, MI, cardiac death/MI and stent thrombosis	Progress reports will be provided to FDA on a quarterly basis

Medtronic will conduct an evaluation of the UADE in accordance with CFR 812.46(b) and shall report the results of such evaluation to FDA and to all reviewing IRBs and participating investigators within 10 working days after Medtronic first receives notice of the effect. Thereafter, Medtronic shall submit such additional reports concerning the effect as FDA requests. Events reported for this study from all geographies will be reviewed and assessed for UADE reporting to the FDA. Events deemed to be UADEs will be submitted per local reporting requirements.

A list of potential adverse events related to the Resolute Onyx™ Zotarolimus-Eluting Coronary Stent System can be found in the Instructions for Use.

8.18. Deviation Handling

A study deviation is defined as an event where the investigator or site personnel did not conduct the study according to the Clinical Investigation Plan, applicable laws or regulations, IRB, or the investigator agreement.

Regulations require that investigators maintain accurate, complete and current records, including documentation of any deviations from the investigation plan including the date of and reason for the deviation. The deviations must be reported to the sponsor on the eCRF.

Investigators are required to obtain prior approval from the Medtronic Clinical Research Department before initiating changes in or deviations from the investigation plan, except where necessary to protect the life or physical well-being of a subject in an emergency. Such approval will be documented in writing and maintained in the study files.

Deviations shall be reported to Medtronic regardless of whether medically justifiable, pre-approved by Medtronic, or taken to protect the subject in an emergency. Deviations to protect the life or physical wellbeing of the subject in an emergency must be reported to Medtronic and the IRB within five working days.

Subject-specific deviations will be reported on the non-compliance eCRF. Deviations that are not subject specific (e.g., unauthorized use of an investigational device by a physician who has not signed an Investigator Agreement) will be reported

to Medtronic in writing. Investigators will also adhere to procedures for reporting study deviations to their IRB in accordance with their IRB requirements.

The study center's compliance with the clinical investigation plan will be assessed on an ongoing basis. Corrective and preventive action plans will be developed and implemented to secure compliance. In cases of serious non-compliance, the sponsor may decide to stop subject enrollment and site participation at an investigational site based on its assessment of repeated occurrences of significant non-compliance.

Examples of deviations include but are not limited to the following:

- Failure to obtain informed consent prior to participation
- Incorrect version of the Informed Consent used
- Failure to obtain IRB approval before the start of the study
- Treated subject did not meet inclusion/exclusion criteria
- Follow-up visit not done
- Reportable adverse events not reported in the required time frame as required by regulation or as specified in protocol
- Source data permanently lost
- Enrollment of patients during lapse of IRB approval

8.19. Subject Withdrawal or Discontinuation

A study subject has the right to discontinue participation in the study at any time without penalty or loss of benefits to which the subject is otherwise entitled. A withdrawn subject will be treated according to standard of medical care and will not be replaced. Subjects will be included in the analyses up to the time that consent was withdrawn.

If an investigator decides to withdraw a subject or if the subject decides to withdraw from the study, the investigator will document the reason for withdrawal, if known, and indicate any rationale for the withdrawal from the study in the subject's file. If a subject is withdrawn from the study due to problems related to the investigational device, continued follow-up may be requested by the sponsor to assess subject safety. In all other cases, no additional data will be captured after the subject withdraws or is removed from the study, unless the information is publicly available. Subjects have the right to withdraw from the study at any time without explaining why and without any consequences.

Subject Lost-To-Follow-Up (LTFU) should be avoided as much as possible and investigators are urged to do their utmost best to maintain subject follow-up compliance. Continuous attempts (e.g., phone, email, certified letter) throughout the final follow-up period should be made to contact the subject, the subject's family or referring physician before documenting a subject LTFU (at least three documented attempts must be made). It is recommended that death study databases (e.g. SSDI) should be checked before subjects are considered LTFU. A subject is not considered LTFU until the subject's final follow-up window has closed. Once a subject has completed their final follow-up visit, a study exit form must be completed.

9. Risks and Benefits

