7.2. Subject Enrollment

A total of 700 subjects in the U.S. are required for this study. Additionally, 100 subjects may be enrolled in Japan. Subjects will be enrolled in up to 70 centers over a 10-month period or until study enrollment is completed. Enrollment parameters are included in the study to avoid introduction of bias to the study results due to disproportionate enrollment.

A maximum of 140 subjects (approximately 20% of the primary analysis population) may be enrolled at one study center. While all sites are expected to contribute to enrollment, there is no set minimum requirement for the number of subjects enrolled at each study center; however, it is expected that a minimum of five (5) subjects will be enrolled per study center.

Medtronic Controlled Information

All subjects who meet eligibility requirements will be asked to participate. Subjects will be considered enrolled into the trial after the following criteria have been met:

1. The signed and dated informed consent has been obtained
2. The patient and target vessel(s)/lesion(s) have met all of the inclusion and none of the exclusion criteria
3. The study stent is introduced into the guide catheter

Subjects who undergo consenting and have confirmation of coronary angiography anatomy eligibility and the Resolute Onyx stent was attempted but was not implanted will be considered part of the intent-to-treat (ITT) population. These subjects will be followed through the one-year endpoint. After the one-year follow-up, the subject will exit the study.

Subjects will complete their participation in the study when all study assessment windows for the duration of the study have passed, subjects have completed all study follow-up assessments, or subject exits the study for other reasons (e.g., investigator withdrawal or subject death). For all subjects, a study exit form will be completed.

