9.1. Potential Risks

This study assesses the use of a shorter duration of DAPT use for a specific patient population treated with DES. Stent drug, stent materials, and technique related standard percutaneous coronary diagnostic and treatment procedures will not be changed. Therefore, the risks associated with this study are related to a reduced duration of DAPT in subjects. As recent evidence have suggested that major bleeding is correlated with adverse events⁴⁶, this study balances the potential risks of shorter DAPT such as a higher risk for thrombotic complications after stent implantation, with the potential benefit of reducing the bleeding risk in a population that is at high risk for bleeding complications. These “high-bleeding risk” patients are estimated to be approximately 15% of those treated for PCI and include patients excluded due to age, underlying comorbidities, (i.e. low ejection fraction, chronic renal insufficiency) and other reasons, who are not able to be subjected to longer term dual antiplatelet therapy use. In many drug-eluting stent studies, these high-bleeding risk patients have been excluded from the study population.

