10.2. Reporting of Adverse Events

Investigators are required to report adverse events and device deficiencies as described in the table below, from the start of procedure until subject’s exit from the study. Reportable adverse events will be reported to the sponsor and documented on the Adverse Event eCRF and in the subject’s medical records. All assessments prior to subject enrollment are considered standard of care.

Reportable events will be followed until the event has resolved (in the case of permanent impairment, the event will be followed until it stabilizes and the overall clinical outcome has been ascertained). The investigator will report events that may occur to the Sponsor, and will assess seriousness, relationship (relatedness to the device, procedure and therapy where applicable), subsequent intervention required, resolution status and whether or not the adverse event resulted in the subject’s discontinuation from the study. The following table outlines the five different levels of causality for every adverse event to be classified against.

Table 8. Causality Assessment⁵³

Not related
	
Relationship to the device or procedures can be excluded when:
 
 - the event is not a known⁵⁴ side effect of the product category the device belongs to or of similar devices and procedures; - the event has no temporal relationship with the use of the investigational device or the procedures; - the serious event does not follow a known response pattern to the medical device (if the response pattern is previously known) and is biologically implausible; - the discontinuation device application or the reduction of the level of activation/exposure – when clinically feasible – and reintroduction of its use (or increase of the level of activation/exposure), do not impact on the serious event; - the event involves a body-site or an organ not expected to be affected by the device or procedure; - the serious event can be attributed to another cause (e.g., an underlying or concurrent illness/clinical condition, an effect of another device, drug, treatment or other risk factors);
---------------------------	---

⁵³ Guidelines on Medical Devices. Clinical Investigations: Serious Adverse Event Reporting Under Directives 90/385/EEC/and 93/42/EEC; MEDDEV 2.7/3 revision 3; May 2015

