12.1.1. Primary Hypothesis

The primary endpoint of the study will be compared to a PG of 9.7%. The study hypotheses are:

$$H_0: \pi \geq 9.7\%$$

$$H_A: \pi < 9.7\%$$

Where π denotes the binary rate of cardiac death and myocardial infarction at one year in a one-month clear population [timeframe: one month to one year]. This one-sided test will be carried out at the 0.025 significance level using the binomial exact test.

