12.1.3. Sample Size Calculation and Methods

Assuming a one-sided alpha level of 0.025 and a true event rate of 6.8%, an effective sample size of 1360 subjects will yield a greater than 97% power to reject the null hypothesis. Assuming a 20% attrition rate, a total sample size of 1700 subjects will be needed.

The outcomes from 700 US subjects enrolled in this study will be combined with those of 1000 subjects from the Resolute Onyx arm of the Onyx ONE Study to form the total sample size of 1700. In addition, subjects enrolled in Japan who have completed their one-year follow-up at the time when the 700 US subjects have completed their one year follow up will also be included in the primary analysis.

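### Protocol 8.19 stops data capture for subjects the investigator removes while consent still stands, which conflicts with 10.2 for events open at removal and needlessly loses later non-fatal endpoint events

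*Protocol*

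**What the plan says.** Protocol 8.19 names two ways out of the study: the subject's own decision and the investigator's. Section 7.2 also lists withdrawal by the investigator as a form of exit. Neither section limits the investigator's reasons.

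If the withdrawal is due to problems with the device, 8.19 lets the sponsor ask for continued follow-up. Then: "In all other cases, no additional data will be captured after the subject withdraws or is removed from the study", unless the information is public. The same section ties the analysis cut-off to withdrawal of consent, so it gives no cut-off for a removed subject who still consents.

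Protocol 10.2 says: "Reportable events will be followed until the event has resolved". Permanent impairment is followed until it stabilises. Section 10.2 has no exception for subjects who have left, and it asks the investigator to record whether the event led to discontinuation. The period for reporting events, however, ends at study exit.

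The primary test compares a single arm with a fixed 9.7% goal "using the binomial exact test" (Protocol 12.1.1; SAP 6.4.1). SAP 6.4.2 keeps in the denominator any one-month clear subject with a CEC event by one year, or with contact on or after the lower limit of the one-year window. SAP 6.4.5 uses the same criteria for complete data, and plans best-case, worst-case and, if needed, tipping-point analyses for the rest.

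**The concern.** Withdrawn consent is a good reason to stop collecting data. Removal by the investigator is not the same thing: consent stands, and the later contacts are by telephone, e-mail or office visit. The documents give no reason for treating the two alike.

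Two consequences follow. First, if a reportable event is open when a subject is removed for a reason not related to the device, a site cannot both stop capture under 8.19 and follow the event under 10.2. Second, later MIs in that subject are not collected. There is no control arm in which a similar loss could offset this, so if removed subjects are at higher risk the observed rate is too low against the fixed goal.

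The device-related exception also fits the study's purpose poorly. Section 9.1 says that "the risks associated with this study are related to a reduced duration of DAPT in subjects", yet a removal connected with the regimen rather than the device has no route to continued follow-up.

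**Working it through.** **The two rules for a removed, consenting subject (reason not device-related)**

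| Situation | 8.19 | 10.2 | Consistent? |
|---|---|---|---|
| Reportable event open at removal | no further capture, unless public | follow to resolution or stabilisation | No |
| New event after exit | no further capture, unless public | reporting period has ended | Yes |

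The strict contradiction is therefore confined to open events. The loss of later endpoint events is a design weakness on which the two sections agree.

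**The plan's own figure.** Protocol 12.1.3 states that "an effective sample size of 1360 subjects will yield a greater than 97% power to reject the null hypothesis", with a true rate of 6.8% and one-sided alpha 0.025. Let c be the largest count with P(X ≤ c | 1360, 0.097) ≤ 0.025.
- c = 110 (110/1360 = 8.09%).
- Actual alpha = P(X ≤ 110 | 1360, 0.097) = 0.0227.
- Power = P(X ≤ 110 | 1360, 0.068) = 97.1%. The stated power reproduces.

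**Subjects governed by 8.19.** Of the 1700, 700 are US subjects in this study and 1000 come from the Resolute Onyx arm of another trial (Protocol 12.1.3; SAP 5.1), whose withdrawal rules are not in these documents. With the planned 20% attrition, 700 × 0.80 = 560, and 560/1360 = 41%. Any Japanese subjects would add to this.

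**Illustration.** The documents give neither a removal rate nor an event rate after removal. I assume 1–3% removed and a 20–30% rate of uncaptured events among them:
- k = 0.01 × 560 ≈ 6 to k = 0.03 × 560 ≈ 17 subjects.
- Uncaptured events = k × r: 6 × 0.20 = 1.2 to 17 × 0.30 = 5.1, against 0.068 × 1360 ≈ 92 expected in all.

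For the false-pass probability, set the true overall rate at 9.7%. The rate in the remaining subjects is p = (1360 × 0.097 − k·r)/(1360 − k). For example, (131.92 − 5.1)/1343 = 0.0944 for k = 17, r = 0.30.

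(a) Removed subjects leave the denominator: P(X ≤ c′ | 1360 − k, p), where c′ is the critical count for 1360 − k subjects.

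(b) Removed subjects stay in as event-free: P(X ≤ 110 | 1360 − k, p), because they add to the denominator but cannot add an event.

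| k | r | p | c′ | (a) | (b) |
|---|---|---|---|---|---|
| 6 | 20% | 0.0965 | 109 | 2.3% | 2.9% |
| 6 | 30% | 0.0961 | 109 | 2.6% | 3.3% |
| 17 | 20% | 0.0957 | 108 | 2.9% | 4.5% |
| 17 | 30% | 0.0944 | 108 | 4.1% | 6.2% |

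The baseline is 2.3%. If removed subjects have the same 9.7% risk as the rest, (a) gives 2.0% for both k = 6 and k = 17. Under (a) the excess therefore depends on removal being linked to risk.

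**Why (b) is possible.** Under SAP 6.4.2 and 6.4.5, any CEC event by one year makes a subject complete. The SAP does not say whether an adjudicated bleed is such an event. If it is, a subject removed after a bleed, with no primary event recorded, counts as event-free and does not enter the worst-case analysis.

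**What the worst-case analysis does when it applies.** If the removed subjects are classed as missing and counted as events, passing requires at most 110 − k events in the others. At a true 9.7% this has probability P(X ≤ 110 − k | 1360 − k, p): about 0.7–0.8% for k = 6 and below 0.1% for k = 17. A wrong pass under (a) would usually be exposed; under (b) the analysis never reaches these subjects.

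**The case against.** The strongest reply is that the plan leans towards keeping subjects and already provides for missing data. Much of this stands.

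- **A reader might infer that a bleed or a departure from the antiplatelet regimen leads to removal.** The documents do not say so. Protocol 5 marks departures from the DAPT duration as deviations, and Protocol 5, 8.7, 8.9 and 8.10 follow subjects given non-study devices and treatment failures through one year. Section 8.19 concerns leaving the study, not stopping a drug. It permits removal for any reason but does not call for it.
- **A reader might apply the rule to all 1360 subjects.** With the same assumed rates, that gives 14–41 removed, 3–12 lost events and a false-pass probability of 3.2–10.2%. It would apply 8.19 to another trial's subjects, about 800 of the 1360, so those figures are not supported.
- **A reader might count every serious event before removal as a threat to the primary rate.** An MI after month one is already in the numerator. A stroke, a non-periprocedural MI or a DAPT interruption of more than three days in month one puts the subject outside the one-month clear population. The exposure is mainly in subjects removed after month one without a prior MI.
- **Deaths need not be lost.** Public information may still be captured, and the glossary classes death of unknown cause as cardiac. The uncaptured events are mainly non-fatal, so the 1–5 above is on the high side to the extent that it includes deaths.
- **The plan has sensitivity analyses.** Data before exit are kept, Protocol 12.10 censors time-to-event outcomes at discontinuation, and SAP 6.4.5 has a worst case. This holds only for subjects classed as missing.

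None of this removes the conflict over open events, or explains why capture should stop while consent stands.

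**Conclusion.** The point holds in limited form. Section 8.19 does not separate withdrawn consent from removal by the investigator, and it contradicts 10.2 for reportable events open at a removal that is not device-related. Neither statement needs an assumption.

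The loss of later non-fatal endpoint events is a real but probably modest weakness. Its size rests on three assumptions: 560 evaluable subjects under this protocol, 1–3% of them removed, and a 20–30% event rate in those removed. The false-pass probability is then about 2.3–4.1%, or about 2.9–6.2% if an earlier CEC event keeps these subjects in the denominator as event-free, against 2.3% at baseline. The documents do not support reading this as a systematic loss of subjects who bleed or leave the regimen, or as a threat across the whole pooled sample. The change is worth making because it is specific and cheap.

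**What to change.** 1. In Protocol 8.19, limit the no-capture rule to withdrawal of consent, and then keep only what consent and public sources allow.
2. For removal by the investigator with consent in place, whatever the reason, continue the scheduled contacts or a record review through one year, and through two years where that was planned.
3. Reconcile 8.19 with 10.2 so that reportable events open at removal are followed to resolution or stabilisation.
4. In SAP 6.4.2 and 6.4.5, class a removed subject with no primary event and no one-year status as missing, even with another CEC event on record, so that the worst-case and tipping-point analyses cover them.

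The cost is a change of wording in the protocol, consent form and SAP, and continued site contact with a few subjects. No new visits are needed.
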